SUD period: defined as the period between a patient's first 44mg/1.1mL vial of elranatamab and first 76mg/1.9mL vial of elranatamab, inclusive. See Section 9.3.1 and Annex 1 for more details. Within the SUD period, three sub-periods are identified:

- **Overall:** defined as the period between first 44mg/1.1mL vial and first 76mg/1.9mL vial of elranatamab.
- **First 44mg/1.1mL vial – Second 44mg/1.1mL vial:** defined as the period between the two 44mg/1.1mL vials of elranatamab, if second 44mg/1.1mL vial is administered.
- **Second 44mg/1.1mL vial – first 76mg/1.9mL vial:** defined as the period between the second 44mg/1.1mL vial and the first 76mg/1.9mL vial of elranatamab, if second 44mg/1.1mL vial is administered.

Follow-up period: defined as the period between the first hospital claim for elranatamab (index date) and the end of the hospital claim of the last elranatamab administration. Within this follow-up period, five sub-periods are identified (when sufficient follow-up time is available at the patient level). These sub-periods allow for reporting study endpoints across different phases of the follow-up period, and are based on expected dosing administrations and schedule of patients with switch to bi-weekly administrations from label guidance (see [Table 10. Dosing Schedule of Elranatamab during Follow-up Period for Patients Switching to](#)

[Q2W](#) and [Table 11. Dosing Schedule of Elranatamab during Follow-up Period for Patients staying on QW](#)):

- **Index date to day 8:** defined as the first 8 days post-index date, inclusive. Also defined as day 1 to day 8.
- **Day 9 to day 168:** defined as the period from day 9 to day 168 post-index date.
- **Day 169+:** defined as the period from day 169 post-index date to end of follow-up period.

- **Overall follow-up:** defined as the period from index date to end of follow-up period.

IVIG follow-up assessment period: defined as the 30-day window post index date. If a patient has fewer than 30 days of data available post to the index date, the assessment window will be equal to the maximum number of days available post to the index date.

CRS/ICANS follow-up assessment period: defined as the 14-day window post index date. If a patient has fewer than 14 days of data available post to the index date, the assessment window will be equal to the maximum number of days available post to the index date.

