9.3.1 Exposure Groups and Assessment Periods

[Table 1](#) outlines the variables to define exposure groups that will be used to identify patients and stratify analyses.

Table 1. Variables for Exposure

Variable	Role	Data Source	Operational Definition	
			Definition	Assessment Period(s)
Study population	Exposure	MDV	All patients with MM who have a hospital claim for elranatamab after March 26, 2024, and who meet the inclusion and exclusion criteria outlined in Sections 9.2.1 and 9.2.2.	Index date
SUD Exposure Group	Exposure	MDV	
Group A: Complete and timely SUD period
 
Patients in the study population with two 44mg/1.1mL vials (second 44mg/1.1mL vial is received 1 to 7 days after the first) and one subsequent 76mg/1.9mL vial between 1 to 7 days after second 44mg/1.1mL vial
 
Group B: Complete but not timely SUD period
 
Patients in the study population with two 44mg/1.1mL vials and one subsequent 76mg/1.9mL vial after the second 44mg/1.1mL vial, with one or both intervals between doses ranging from 8 to 14 days.
 
Group C: Alternative SUD period
 
 • Only one 44mg/1.1mL vial: patients in the study population with only one 44mg/1.1mL vial prior to receiving a 76mg/1.9mL vial • More than two 44mg/1.1mL vials: patients in the study population with more than 	SUD period

090177e1a4a71ff1\Approved\Approved On: 05-Nov-2025 14:15 (GMT)

Variable	Role	Data Source	Operational Definition	
			Definition	Assessment Period(s)
			
two 44mg/1.1mL vials prior to receiving a 76mg/1.9mL vial
 
 Extremely untimely: patients in the study population with more than 14 days between the first and second 44mg/1.1mL vial or between the second 44mg/1.1mL vial and the first 76mg/1.9mL vial 
Note that patients who received only 44mg/1.1mL vials or only 76mg/1.9mL vials are not classified under any SUD exposure group but will remain part of the study population.
	

Figure 2 illustrates possible elranatamab administration scenarios for each SUD group. These examples are not exhaustive and do not represent all potential administration schedules.

090177e1a4a71ff1\Approved\Approved On: 05-Nov-2025 14:15 (GMT)

Figure 2. SUD Periods Administration Schedule

[figure not shown]

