			Number of all-cause ED claims PPPM. Reported for all patients and for patients with ≥ 1 all-cause ED claim.	HCRU baseline period Follow-up period (overall only)
			Number of all-cause ED claims PPPD. Reported for all patients and for patients with ≥ 1 all-cause ED claim.	SUD period
Any HCRU (IP, OP, and ED) claim [Summary statistic]	Outcome	MDV	Number of patients with ≥ 1 all-cause HCRU (IP, OP, and ED) claim (yes/no)	HCRU baseline period SUD period Follow-up period (overall only)
			Number of all-cause HCRU claims PPPM. Reported for all patients and for patients with ≥ 1 all-cause HCRU claim.	HCRU baseline period Follow-up period (overall only)
			Number of all-cause HCRU claims PPPD.	SUD period

090177e1a4a71ff1\Approved\Approved On: 05-Nov-2025 14:15 (GMT)

Variable	Role	Data Source	Operational Definition	
			Definition	Assessment Period(s)
			Reported for all patients and for patients with ≥ 1 all-cause HCRU claim.	
Cost of IP claims [Summary statistic]	Outcome	MDV	Total cost of IP claims PPPM	HCRU baseline period Follow-up period (overall only)
			Total cost of IP claims PPPD	SUD period
Cost of OP claims [Summary statistic]	Outcome	MDV	Total cost of OP claims PPPM	HCRU baseline period Follow-up period (overall only)
			Total cost of OP claims PPPD	SUD period
Cost of ED claims [Summary statistic]	Outcome	MDV	Total cost of ED claims PPPM	HCRU baseline period Follow-up period (overall only)
			Total cost of ED claims PPPD	SUD period
Cost of HCRU claims [Summary statistic]	Outcome	MDV	Total cost of all-cause HCRU claims PPPM	HCRU baseline period Follow-up period (overall only)

090177e1a4a71ff1\Approved\Approved On: 05-Nov-2025 14:15 (GMT)

Variable	Role	Data Source	Operational Definition	
			Definition	Assessment Period(s)
			Total cost of all-cause HCRU claims PPPD	SUD period
Total duration of all-cause IP claims	Outcome	MDV	The total time in days of IP stays among patients who have at least 1 IP stay (continuous).	HCRU baseline period Follow-up period
Duration of all-cause IP claims	Outcome	MDV	Days of IP stays among patients who have at least 1 IP stay PPPM	HCRU baseline period Follow-up period
Department visits claims [Summary statistic]	Outcome	MDV	Number of patients with top 5 most common department visits claims (yes/no) Note that the top 5 will not be established a priori, but rather will be determined based on the data and sample	HCRU baseline period SUD period Follow-up period (overall only)

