9.7.4. Healthcare Resource Utilization and Costs

All-cause HCRU will be measured as the total number IP, OP, and ED that occurred over the follow-up period. Health claims will only be counted once per day to estimate visits. Additionally, the total length of IP stays will be reported among patients with at least one IP visit. Costs will be adjusted for inflation. More details will be provided in the SAP.

PPPM

PPPM standardizes HCRU and cost by calculating the average of a specific variable or a number of specific events (e.g., ED health claims, IP health claims) per month for each patient. In this study, PPPM will be used to report ED, IP and OP visits and cost for the HCRU baseline period and the follow-up period. To obtain PPPM, the following formula will be used for each patient:

$$PPPM = \frac{\text{Total number of events during a specified period}}{\text{Duration of the specified period (in months)}}$$

PPPD

PPPD standardizes HCRU and cost by calculating the average of a specific variable or a number of specific events (e.g., ED health claims, IP health claims) per day for each patient. In this study, PPPD

090177e1a4a71ff1\Approved\Approved On: 05-Nov-2025 14:15 (GMT)

will be used to report ED, IP and OP visits and cost for the SUD period. To obtain PPPD, the following formula will be used for each patient:

$$PPPD = \frac{\text{Total number of events during a specified period}}{\text{Duration of the specified period (in days)}}$$

This calculation will allow meaningful comparisons across patients with varying assessment period lengths, by normalizing resources use to a monthly rate. Summary statistics (mean, median, min, max) will then be reported to understand average monthly cost and utilization patterns across patients.

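### SUD-period costs and claim counts are planned only as daily rates over the interval that defines the step-up groups, so the cost of completing step-up is never shown and timely step-up tends to look dearer

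*Protocol*

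**What the plan says.** - **Metric.** Section 9.7.4 states that PPPD "will be used to report ED, IP and OP visits and cost for the SUD period". It is calculated for each patient as events (or cost) in the period divided by that patient's days in the period.
- **Cost rows.** In Table 5 (section 1.1.2), each SUD cost row is a daily rate, for example "Total cost of IP claims PPPD" and "Total cost of all-cause HCRU claims PPPD". The PPPM cost rows cover the HCRU baseline period and overall follow-up, which Table 2 assigns to the whole study population.
- **Claim rows.** SUD claim counts are also PPPD, next to a yes/no row. Total inpatient days are assessed for baseline and follow-up only.
- **Divisor.** Section 9.2 defines the SUD period as running between a patient's "first 44mg/1.1mL vial of elranatamab and first 76mg/1.9mL vial of elranatamab, inclusive".
- **Groups.** In Table 1, Group A has both gaps at 1 to 7 days. Group B has the same vials "with one or both intervals between doses ranging from 8 to 14 days". Table 12 gives A, B and the extremely untimely part of C the same content: 2 x 44 mg and 1 x 76 mg. The other two parts of C have one 44 mg vial, or three or more.
- **Display.** Table 2 shows SUD outcomes for Group A, Group A+B and Group C.
- **Justification.** After the PPPD formula, section 9.7.4 adds: "This calculation will allow meaningful comparisons across patients with varying assessment period lengths". The same sentence speaks of a monthly rate, although PPPD is daily.

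**The concern.** A per-day rate suits a resource that accrues with time. A large part of SUD cost does not: the vials are fixed per completed course in Groups A and B. Dividing that fixed amount by the length of the course spreads it thinly over a slow step-up and thickly over a fast one. Because course length is also what separates A from B, the divisor carries the exposure contrast into the outcome.

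Objective 3 is to describe cost in the SUD period. As planned, a reader gets no figure for what it costs to bring a patient through step-up, and the daily figures by group invite the conclusion that timely step-up is the more expensive pattern. Nothing else in Table 5 would correct that impression.

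**Working it through.** The protocol gives no prices and no cost figure, so there is nothing to reproduce. The check uses its PPPD formula with stated assumptions.

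**1. Period lengths (Table 1, counted inclusively).** Length = gap 1 + gap 2 + 1.
- Group A: 1+1+1 = 3 to 7+7+1 = 15 days.
- Group B: 8+1+1 = 10 to 14+14+1 = 29 days.
- The ranges overlap at 10 to 15 days.
- With all allowed gap pairs weighted equally (assumption), A has 49 pairs with mean 4+4+1 = 9.0 days. B has 196 − 49 = 147 pairs with mean (196 × 16 − 49 × 9)/147 = 18.3 days.

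**2. Model.** Let D be the vial cost per course, h the other cost per day (the same in both groups, assumption) and L the inclusive length.
- Total = D + hL, which rises with L.
- PPPD = D/L + h, which falls with L.

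**3. Worked case.** Assume price proportional to mg, with one 44 mg vial as the unit: D = 2 + 76/44 = 3.73. Take L = 8 for A (Tables 10 and 11 place the three step-up administrations by day 8), L = 18 for B (near the mean above) and h = 0.2.
- A: PPPD = 3.73/8 + 0.2 = 0.67; total = 3.73 + 8 × 0.2 = 5.3.
- B: PPPD = 3.73/18 + 0.2 = 0.41; total = 3.73 + 18 × 0.2 = 7.3.

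**4. The contrast that Table 2 displays (A against A+B).** The share in B is not given, so a range is shown, still with h = 0.2.

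| Share in B | PPPD, A | PPPD, A+B | Ratio | Total, A | Total, A+B |
|---|---|---|---|---|---|
| 10% | 0.67 | 0.64 | 1.04 | 5.3 | 5.5 |
| 20% | 0.67 | 0.61 | 1.08 | 5.3 | 5.7 |
| 50% | 0.67 | 0.54 | 1.24 | 5.3 | 6.3 |

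For 20%: 0.8 × 0.666 + 0.2 × 0.407 = 0.61, and 0.8 × 5.33 + 0.2 × 7.33 = 5.7.

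**5. Range over h (20% in B).**
- h = 0: PPPD 0.47 against 0.41 (ratio 1.13), with equal totals of 3.73.
- h = 1: PPPD 1.47 against 1.41 (ratio 1.04), with totals 11.7 against 13.7.

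The PPPD ratio shrinks as other costs grow, but its direction stays opposite to that of the totals whenever h > 0.

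**6. What would offset it.** At 8 against 18 days, PPPD is equal if daily other cost in B exceeds that in A by 3.73/8 − 3.73/18 = 0.26 units. That is 26% more if h in A is 1, or 2.3 times as much if h in A is 0.2.

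**7. Can the reader recover the total from SUD length?** Table 4 reports days from first 44 mg to first 76 mg vial. However, PPPD is averaged over per-patient ratios. On the equally weighted Group A grid, with vial cost 100 and no other cost, mean PPPD is 12.59 and mean length is 9.0. Their product is 113, while the true mean total is 100.

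**The case against.** The other side has several sound points.

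- **The study is descriptive, with no formal group comparisons.** This stands. The issue is a summary that can mislead, not a faulty test. The comparability sentence speaks of patients rather than exposure groups, but the SUD results are laid out by group and will be read that way.
- **B is never shown alone.** This stands. A reader might take the A against B drug ratio (18/8 = 2.25 in the worked case) as the size of the distortion. Table 2 does not display that contrast, and A against A+B is much milder.
- **Reversal is not guaranteed.** This stands. A reader might infer that timely step-up must look dearer for any positive costs. That also needs similar daily cost in the two groups and a shorter period in A. The protocol gives no basis for equal daily cost, and lengths overlap at 10 to 15 days.
- **Group C lies outside the argument.** This stands for pooled C, where vial counts vary, so the direction for A against C is open.
- **Outpatient visits per day need not behave the same way.** This stands. Three administrations fix a number of outpatient visits only if they are given as outpatient, and Table 3 records care setting as either.
- **Total SUD cost has its own length effect.** This stands. In the model, B's extra 2.0 units are ten more days at 0.2. A patients also incur daily cost on those days, after their window has closed. The total answers what completing step-up costs; it is not a neutral ranking of the groups.
- **SUD length is in Table 4, and cost detail is deferred to the SAP.** This helps only in part. Length shows that the groups differ but does not give the mean total, and the protocol itself fixes PPPD as the SUD metric.

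**Conclusion.** The point holds in a limited form. Table 5 and section 9.7.4 give SUD-period cost and claim counts only per day, over the interval whose gaps define Groups A and B, although the vials are the same in both. The plan therefore never reports the cost of completing step-up, and at similar daily non-drug cost its daily figure tends to make timely step-up look dearer even when its total is lower.

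In the displayed A against A+B contrast the effect is modest: a PPPD ratio of about 1.08 in the worked case, and 1.04 to 1.24 for 10% to 50% in B. This rests on assumed prices, lengths, daily cost and share in B, and on elranatamab cost being inside the claim costs, from which Table 5 excludes nothing. It is a reporting weakness in a secondary objective that is worth correcting. It does not show that the planned results will rank the groups wrongly.

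**What to change.** - In Table 5, for the overall SUD period and by exposure group, add total cost per patient and total IP, OP and ED claims per patient. Show SUD length beside them.
- Preferably add total cost per patient over one common fixed window from index, because total SUD cost itself rises with period length. Label it as a different question: Tables 10 and 11 expect further 76 mg administrations after step-up, so patients who finish early will have more vials in that window.
- Keep the PPPD rows.
- In section 9.7.4, remove the comparability statement for SUD-period PPPD, or limit it by noting that the divisor also defines the groups. Correct the reference to a monthly rate where PPPD is meant.

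The cost is a few extra table rows. The SUD totals are already the PPPD numerators, and SUD length is already derived for Table 4. Only the fixed-window row needs a new derivation.

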9.7.5. Subgroup analyses

A subgroup analysis will be conducted for patients identified as having low body weight at index date. The threshold defining "low weight" will be specified in detail within the SAP, based on clinical guidance.

This subgroup analysis will replicate the primary objectives (Objective 1 and Objective 2), as well as secondary objectives 5 and 6, which focus on known adverse events and infections following elranatamab administration.

9.7.6. Sensitivity analyses

No sensitivity analysis will be conducted as a part of this analysis.

9.8. Quality Control

STATLOG will code measures for patient identification, and study endpoints based on codes and algorithms described in this protocol and corresponding SAP. This protocol will be strictly followed when conducting the analysis of this study. All cohorts developed, statistical analyses implemented, and tables completed will undergo quality control review by at least one additional analyst or scientist under the supervision of the Study Lead. The Study Lead will review all results tables and other final deliverables to confirm accuracy, logical flow, and appropriate format.

MDV collects and utilizes both personal data and anonymously processed information in strict compliance with the Act on the Protection of Personal Information, the EU's General Data Protection Regulation (GDPR), and other applicable legal frameworks. Recognizing the sensitive nature of medical data, particularly that of patients and healthcare institutions, MDV is committed to ensuring the confidentiality, integrity, and proper use of such information. To this end, MDV implements robust safety management practices, including appropriate technical and organizational security measures, to prevent unauthorized access, data breaches, loss, or alteration of personal information.

In addition to technical safeguards, MDV emphasizes the importance of human factors in data protection. The organization conducts regular training and development programs for its staff to reinforce awareness and adherence to privacy protocols. Furthermore, MDV exercises strict oversight over any third-party entities entrusted with personal data, ensuring that outsourced data management aligns with its stringent security standards. Through these comprehensive measures, MDV upholds a high-level information security management system and demonstrates its ongoing commitment to protecting personal information in the healthcare domain.

9.9. Limitations of the Research Methods

This study is subject to limitations, described below:

- The MDV database follows patients' medical journey through the same facility, not between facilities – as such there is visibility only on prior diagnoses received within the same facility. There may be a loss in data continuity due to hospital transfers, however, patients in Japan tend to be treated in the same centers therefore this may be minimal.
- Measures of MM disease severity, such as ISS stage, M-protein level, and cytogenetic risk are not available in MDV. This limits the extent to which patients' MM can be characterized.
- This study will use a secondary data source. Because of the secondary data source, common limitations apply to this study, including:
 - Data may not be complete or accurate due to potential errors in coding or record-keeping at the point of the healthcare provider.
 - Lags in data availability can lead to inaccuracies in timing of reported information. This can particularly impact estimates over short periods of time (e.g., HCRU on index date).
 - Missing data cannot confirm the absence of a condition or value in a patient's medical history; only that it was not documented.
 - The internal process of obtaining and cleaning data is not fully known by scientists using RW databases, as such the internal validity of RWD remains largely unknown to scientists working with the data (19). Although there are concerns about the validity of RWD, the MDV database still has been used for a large number of peer-reviewed publications (14).
 - The lack of granularity of certain variables can limit the research that can be done; for example, granularity of grade of infection is often not available.
 - Clinical trials have close monitoring and prospective data collection, which RWD lacks. This means that the description of AEs in RW patients is expected to be less precise. Additionally, estimates of incidence and prevalence of safety events are likely to be underestimated compared to clinical trials or prospective studies where timing of assessments can be controlled. However, RWD can be useful to describe incidences of AEs in a larger and more heterogenous samples (20).
- This study population consists Japanese patients treated with elranatamab in Japan; however, the data does not cover all patients in Japan. As such, results may not fully represent the broader experience of patients receiving elranatamab both within Japan and internationally.

9.10. Other Aspects

Not applicable

10. PROTECTION OF HUMAN SUBJECTS

10.1. Patient Information

This study involves data that exist in deidentified/anonymized structured format and contain no patient personal information.

10.2. Patient Consent

As this study involves deidentified/anonymized structured data, which according to applicable legal requirements do not contain data subject to privacy laws, obtaining informed consent from patients by Pfizer is not required.

10.3. Institutional Review Board (IRB)/ Ethics Committee (EC)

Approval from an institutional review board/independent ethics committee is not required for this study as only de-identified secondary data sources will be used. Therefore, this study is considered exempt from the requirements for “human subjects research”.

10.4. Ethical Conduct of the Study

The study will be conducted in accordance with legal and regulatory requirements, as well as with scientific purpose, value, and rigor, and follow generally accepted research practices described in the Guidelines of Good Pharmacoepidemiology Practices (GPP) issued by the International Society for Pharmacoepidemiology (ISPE) (24), Good Practices for Outcomes Research issued by the International Society for Pharmacoeconomics and Outcomes Research (ISPOR) (25), International Ethical Guidelines for Epidemiological issued by the Council for International Organizations of Medical Sciences (CIOMS) (26).

11. MANAGEMENT AND REPORTING OF ADVERSE EVENTS/ADVERSE REACTIONS

This study involves data that exist as structured data by the time of study start. In these data sources, it is not possible to link (i.e., identify a potential association between) a particular product and medical event for any individual. Thus, the minimum criteria for reporting an adverse event (AE) (i.e., identifiable patient, identifiable reporter, a suspect product, and event) cannot be met.

